7.1 Adverse Event (AE)

An AE is any untoward medical occurrence in a patient or clinical trial subject undergoing a trial intervention and which does not necessarily have a causal relationship with this treatment. An AE can therefore be any unfavourable and unintended sign (including an abnormal laboratory finding), symptom, or disease temporally associated with the use of the trial interventions, whether or not considered related to the interventions being evaluated.

i. Adverse Event recording

For the purposes of the study, AEs will be followed up according to local practice until the event has stabilised or resolved, or the Follow-up Visit, whichever is the sooner. All SAEs will be recorded throughout the study and should be reported to the sponsor and any unexpected

Short Title: IP4 - CHRONOS	Protocol No: 19CX5006	Sponsor: Imperial College London	Version: 5.0 Date: 13 th July 2022
			10 daily 2022

and related SAES should also be reported to the REC (as per attached JRCO SOP – appendix 3).

ii. Severity of Adverse Events

Mild: Awareness of event but easily tolerated

Moderate: Discomfort enough to cause some interference with usual activity

Severe: Inability to carry out usual activity

iii. Causality of Adverse Events

Unrelated: No evidence of any causal relationship

- *Unlikely:* There is little evidence to suggest there is a causal relationship (e.g. the event did not occur within a reasonable time after trial interventions). There is another reasonable explanation for the event (e.g. the patient's clinical condition, other concomitant treatment).
- *Possible:* There is some evidence to suggest a causal relationship (e.g. because the event occurs within a reasonable time after administration of the trial interventions). However, the influence of other factors may have contributed to the event (e.g. the patient's clinical condition, other concomitant treatments).
- *Probable:* There is evidence to suggest a causal relationship and the influence of other factors is unlikely.
- *Definite:* There is clear evidence to suggest a causal relationship and other possible contributing factors can be ruled out.

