7.3 Serious Adverse Events (SAE)

i. Definition of SAE

An SAE is defined as any event that:

- Results in death;
- Is life-threatening*;
- Requires hospitalisation or prolongation of existing inpatient hospitalisation**;
- Results in persistent or significant disability or incapacity;
- Is a congenital abnormality or birth defect;

^{* &}quot;Life-threatening" in the definition of "serious" refers to an event in which the subject was at risk of death at the time of the event; it does not refer to an event which hypothetically might have caused death if it were more severe.

Short Title: IP4 - CHRONOS	Protocol No: 19CX5006	Sponsor: Imperial College London	Version: 5.0 Date: 13 th July 2022
			10 daily 2022

** "Hospitalisation" means any unexpected admission to a hospital department. It does not usually apply to scheduled admissions that were planned before study inclusion or visits to casualty (without admission).

Medical judgement should be exercised in deciding whether an adverse event/reaction is serious in other situations. Important adverse events/reactions that are not immediately life-threatening, or do not result in death or hospitalisation but may jeopardise a subject, or may require intervention to prevent one of the other outcomes listed in the definition above should also be considered serious.

List of expected adverse events that may require hospitalisation and serious adverse events that will not require reporting as SAEs but will be collected:

- Urinary retention and any admission required for this
- Urinary tract infection and any admission required for this
- Epididymo-orchitis and any admission required for this
- Dysuria
- Debris in urine and any admission required for this
- Haematuria and any admission required for this
- Erectile dysfunction and any other sexual sequelae side-effects such as dry orgasm, lack of orgasm, poor libido
- Urinary incontinence
- Rectal discomfort, bleeding, diarrhoea
- Recto-urethral fistula and any operations required for this
- Lethargy, tiredness, poor appetite
- Urethral stricture and any operations required for this
- Transurethral resection of prostate and any operations required for this
- Operations required for symptoms of bladder outlet obstruction
- Any expected complication related to post-operative course from radical prostatectomy i.e. lymphocoele, bowel injury, haematoma needing percutaneous drainage

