- Expected toxicity from systemic therapy such as neutropenia, neutropenic sepsis, weight gain, decreased libido, breast tenderness, metabolic syndrome, lethargy, fatigue, osteoporosis, nausea and vomiting, diarrhoea, constipation, muscle/joint pains and hair loss.
- Bowel stricture post radiotherapy, and procedures required for this

ii. Reporting of SAEs

Rapid reporting of all SAEs i.e. within 24 hours, occurring during the study must be performed as detailed in SAE reporting instructions. If the investigator becomes aware of safety information that appears to be intervention related, involving a subject who participated in the study, even after an individual subject has completed the study, this should be reported to the Sponsor.

All SAEs will be reviewed by the Chief Investigator or a designated medically qualified representative to confirm expectedness and causality.

Reporting of SAEs and review by the CI will be via the trial data collection system (CRF/electronic case report form [InForm]).

iii. Related SAEs

Related: results from administration of any research procedures

Short Title: IP4 - CHRONOS	Protocol No: 19CX5006	Sponsor: Imperial College London	Version: 5.0 Date: 13 th July 2022
			10 daily 2022

iv. Unexpected SAEs

Unexpected: type of event is not listed in the protocol as an expected occurrence

v. Reporting of SAEs that are related and unexpected

Please Note: These reporting requirements refer to CHRONOS-A only

An SAE form should be completed on the InForm eCRF within 24 hours. However, relapse, death and/or hospitalisations for elective treatment of a pre-existing condition do not need reporting as SAEs.

All related and unexpected SAEs should be reported to the relevant REC as per the following definition. In the opinion of the Chief Investigator, the event was:

- 'Related', i.e. resulted from the administration of any of the research procedures; and
- 'Unexpected', i.e. an event that is not listed in the protocol as an expected occurrence Reports of related and unexpected SAEs should be submitted within 15 days of the Chief Investigator becoming aware of the event, using the *NRES SAE form for non-IMP studies*. The Chief Investigator must also notify the Sponsor of all SAEs. Local investigators should report any SAEs as required by their Local Research Ethics Committee, Sponsor and/or Research & Development Office.

Contact details of sponsor for reporting SAEs are as follows:

Joint Research Compliance Office:

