^{*}Report serious adverse events for CHRONOS-A and CHRONOS-B separately

¹Where subjects have more than one AE, the highest relationship has been used

²Expected adverse events which will not be reported are listed in Appendix 1

Imperial Clinical Trials Unit	STATISTICAL ANALYSIS PLAN: FEASIBILITY	CHRONOS
----------------------------------	--	---------

Table 2. 21: Summary of Serious Adverse Events by Category, by Treatment Arm*

	Subjects with SAEs					
Treatment	Resulted in death	Life threatening	Required inpatient hospitalisation or prolongation of existing hospitalisation	Resulted in persistent or significant disability/incapacity	Resulted in congenital anomaly/birth defect	Other medically important event
	xxx (xx%)	xxx (xx%)	xxx (xx%)	xxx (xx%)	xxx (xx%)	xxx (xx%)
	xxx (xx%)	xxx (xx%)	xxx (xx%)	xxx (xx%)	xxx (xx%)	xxx (xx%)
	xxx (xx%)	xxx (xx%)	xxx (xx%)	xxx (xx%)	xxx (xx%)	xxx (xx%)
Total	xxx (xx%)	xxx (xx%)	xxx (xx%)	xxx (xx%)	xxx (xx%)	xxx (xx%)

	All SAEs					
Treatment	Resulted in death	Life threatening	Required inpatient hospitalisation or prolongation of existing hospitalisation	Resulted in persistent or significant disability/incapacity	Resulted in congenital anomaly/birth defect	Other medically important event
	xxx (xx%)	xxx (xx%)	xxx (xx%)	xxx (xx%)	xxx (xx%)	xxx (xx%)
	xxx (xx%)	xxx (xx%)	xxx (xx%)	xxx (xx%)	xxx (xx%)	xxx (xx%)
	xxx (xx%)	xxx (xx%)	xxx (xx%)	xxx (xx%)	xxx (xx%)	xxx (xx%)
Total	xxx (xx%)	xxx (xx%)	xxx (xx%)	xxx (xx%)	xxx (xx%)	xxx (xx%)

^{*}Report serious adverse events for CHRONOS-A and CHRONOS-B separately

Imperial Clinical
Trials Unit

STATISTICAL ANALYSIS PLAN: FEASIBILITY

CHRONOS

Table 2. 22: Number of Serious Adverse Events by Causality Relationship to event, by Treatment Arm*

	Subjects with SAEs							
Treatment	Definitely	Probably	Possibly	Unlikely	Not	Not	Total	
					related	assessable		
	xxx (xx%)	xxx (xx%)	xxx (xx%)	xxx (xx%)	xxx (xx%)	xxx (xx%)	xxx (xx%)	
	xxx (xx%)	xxx (xx%)	xxx (xx%)	xxx (xx%)	xxx (xx%)	xxx (xx%)	xxx (xx%)	
	xxx (xx%)	xxx (xx%)	xxx (xx%)	xxx (xx%)	xxx (xx%)	xxx (xx%)	xxx (xx%)	
Total	xxx (xx%)	xxx (xx%)	xxx (xx%)	xxx (xx%)	xxx (xx%)	xxx (xx%)	xxx (xx%)	

	All SAEs						
Treatment	Definitely	Probably	Possibly	Unlikely	Not	Not	Total
					related	assessable	
	xxx (xx%)	xxx (xx%)	xxx (xx%)	xxx (xx%)	xxx (xx%)	xxx (xx%)	xxx (xx%)
	xxx (xx%)	xxx (xx%)	xxx (xx%)	xxx (xx%)	xxx (xx%)	xxx (xx%)	xxx (xx%)
	xxx (xx%)	xxx (xx%)	xxx (xx%)	xxx (xx%)	xxx (xx%)	xxx (xx%)	xxx (xx%)

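### Protocol 7.3 v exempts death, without qualification, from SAE reporting in CHRONOS-A, contradicting the SAE definition and reporting rules elsewhere in the protocol and SAP

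*Protocol*

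**What the plan says.** Protocol 7.3 v covers SAEs that are related and unexpected. It opens by limiting its scope: "These reporting requirements refer to CHRONOS-A only". It asks for an SAE form on the eCRF within 24 hours and then makes an exception: "relapse, death and/or hospitalisations for elective treatment of a pre-existing condition do not need reporting as SAEs".

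The provisions around it say the following.

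- Protocol 7.3 i lists the criteria for an SAE, and the first is "Results in death". SAP 8.2 repeats the definition.
- Protocol 7.1 i: "All SAEs will be recorded throughout the study and should be reported to the sponsor".
- Protocol 7.3 ii: "Rapid reporting of all SAEs i.e. within 24 hours, occurring during the study must be performed as detailed in SAE reporting instructions". It also has the Chief Investigator, or a medically qualified delegate, review every SAE for expectedness and causality, using the trial data collection system.
- Protocol 7.3 v, after the exception: "All related and unexpected SAEs should be reported to the relevant REC as per the following definition". It sets 15 days for that report and requires the Chief Investigator to tell the Sponsor of every SAE.
- SAP Table 2.21, to be produced separately for each trial, has a column headed "Resulted in death". SAP Table 2.22 gives SAEs by causal relationship and arm.

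**The concern.** The exemption removes from SAE reporting an event that the same section treats as the first mark of seriousness. Nothing limits it to death from prostate cancer or to death unrelated to treatment. As worded, it covers a death caused by prostatectomy, radiotherapy or focal therapy.

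Two things are at stake. The first is timeliness: if no SAE form is filed, the 24-hour report and the causality review that follows from it may not begin. The second is completeness. Protocol 8.3 iv and SAP 9.8 both build the safety analysis on SAE frequency, so a death never entered as an SAE could be missing from the tables that compare safety between the CHRONOS-A arms.

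**Working it through.** No arithmetic applies. The check sets the provisions side by side.

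1. **Scope of the exemption.** The sentence lists three items: relapse, death, and certain hospitalisations. The phrase about elective treatment of a pre-existing condition can sensibly attach only to hospitalisations. Death therefore stands unqualified, and 7.3 v applies to both CHRONOS-A arms.

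2. **Against the definition.** Under 7.3 i and SAP 8.2 a death is an SAE. Under 7.3 v it need not be reported as one. Both cannot guide the same site.

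3. **Against the general reporting rules.** Sections 7.1 i and 7.3 ii apply to all SAEs, with no exception for death. A site could reasonably take the specific exception in 7.3 v to override them for CHRONOS-A, but the text does not say which prevails.

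4. **Within 7.3 v.** The sentences that follow the exception require Sponsor notification of all SAEs and REC reporting of related, unexpected ones. A treatment-related, unexpected death meets both, yet it has just been exempted from the form that would bring it to notice.

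5. **Do the expected-event lists explain it?** No. Death is neither in the 7.3 list of events that are collected but not reported as SAEs, nor in SAP Appendix 1. Those listed events are explicitly still to be collected; 7.3 v makes no such provision for death.

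6. **Against the SAP output.** Table 2.21 presupposes that CHRONOS-A deaths arrive as SAEs. If 7.3 v is followed literally, its deaths column, and the matching entries in Table 2.22, could show none even though deaths had occurred.

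7. **What else could capture a death.**
   - *Intervention-related safety information (7.3 ii).* This goes to the Sponsor, even after a participant has completed the study. It depends on someone judging the event to be intervention related, and the sentence sets no time limit.
   - *An earlier SAE.* A complication that was life-threatening or caused an unexpected admission qualifies in its own right, and Table 2.20 would show its outcome. This fails where death is the first reportable event. It also fails where the complication is on the expected-event list: bowel injury after prostatectomy, for example, is on that list and so is not reported as an SAE.
   - *AE Tables 2.17 to 2.19.* These give grade (up to 5) and relationship by arm. They carry no 24-hour clock, and the footnotes to Tables 2.18 and 2.19 leave out the events in Appendix 1.
   - *Withdrawal Table 2.12.* It has a row for death, by trial only, without arm or causality.
   - *Main-stage endpoints.* All-cause mortality is a secondary endpoint (Protocol 2.6). PFS in CHRONOS-A counts only prostate cancer mortality (Protocol 2.5), and patients without an event are censored (Protocol 8.3). A treatment-related death from another cause is therefore not a PFS event. The feasibility SAP's secondary variables (8.4) are questionnaires only.

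Each route could record some deaths. None reliably provides both a 24-hour report of the death and an entry in Table 2.21.

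**The case against.** The strongest reply is that one sentence should not be read in isolation. Several rules still point towards reporting a treatment-related death: 7.1 i, 7.3 ii, and the Sponsor and REC sentences of 7.3 v. Being exempt from reporting as an SAE is not the same as going unrecorded, since AE listing continues. Day-to-day practice follows SAE reporting instructions and a sponsor SOP, neither of which is among the documents, and these may handle deaths properly. The intention may simply have been to avoid duplicate reports of disease-related deaths already counted as endpoints.

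Much of this stands. The defect is a conflict between instructions, not a rule set that uniformly drops deaths. A reader might infer more than the text allows in four respects:

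- *That every CHRONOS-A death would go unreported.* The counter-rules and other routes above do not support that.
- *That the oversight committee would be denied timely notice.* No provision sends individual SAE reports to it. Protocol 11.3 describes a combined committee meeting twice a year, and the reporting recipients named in 7.3 are the Sponsor, the Chief Investigator and the REC.
- *That stopping for a harmful arm depends on these reports.* Protocol 11.4 speaks of early evidence of harm and does not mention SAE reports. Fatal SAEs would be an obvious part of such evidence, but that is inference.
- *That the sponsor chose to exempt treatment-related deaths.* Nothing shows this. The text reads as an inconsistency.

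What the reply does not do is remove the contradiction. If only disease-related deaths were meant, 7.3 v does not say so, and instructions held elsewhere do not correct the protocol.

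**Conclusion.** The point holds as an internal contradiction with a possible safety consequence. Protocol 7.3 v conflicts with 7.3 i, 7.1 i, 7.3 ii and SAP 8.2, and with its own later sentences. Followed literally, it could leave a treatment-related CHRONOS-A death without an SAE form, without prompt causality review, and absent from SAP Tables 2.21 and 2.22.

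The size cannot be estimated: the documents give no expected number of treatment-related deaths and no indication of how sites read the sentence. The rule governs all CHRONOS-A participants (60 planned in the pilot, 1190 in the main study). That is the number to whom the wording applies, not a count of deaths that would be missed. CHRONOS-B is outside 7.3 v and has an explicit seven-day limit for fatal SUSARs in 7.3 viii.

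The conclusion assumes that sites act on the protocol as written and that the unseen reporting instructions do not override the exemption. If those instructions already require all deaths to be reported, the practical risk is small, but the protocol text still needs correcting.

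**What to change.** Reconcile 7.3 v with 7.3 i and ii, SAP 8.2 and SAP Table 2.21 in one of two ways:

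- remove death from the list of exempt events; or
- limit the exemption in terms to deaths attributed to prostate cancer that are captured as a PFS event, and state that all other deaths follow 7.3 ii.

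If the second option is taken, add a footnote to Tables 2.21 and 2.22 saying which deaths are excluded and where they are counted. Check that the SAE reporting instructions and the sponsor SOP say the same.

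The cost is one phrase in the protocol, processed as an amendment, and a few more SAE forms. The design, sample size and primary analysis do not change.

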7.4 Annual Progress Reports

Annual Progress Reports will be submitted to the Research Ethics Committee, the Regulatory Authority and the Sponsor in accordance with local requirements. The Annual Progress Reports will detail all SAEs recorded.

7.5 Pregnancy

Not application as the study population is male.

7.6 Reporting urgent safety measures

If any urgent safety measures are taken the CI/Sponsor shall immediately and in any event no later than 3 days from the date the measures are taken and give written notice to the MHRA, the relevant research ethics committee (REC) as well as the sponsors of the measures taken and the circumstances giving rise to those measures. The sponsor in any case should also be informed of urgent safety measures.

8. STATISTICAL ANALYSES

8.1 Sample Size and power considerations

8.1.1 Feasibility and Pilot Stage

For both CHRONOS-A and CHRONOS-B feasibility is considered in terms of recruitment rate, the acceptability of the trial randomisation and adherence to arm allocation.

- CHRONOS-A: A two-arm RCT will recruit 1190 patients over a total recruitment and follow-up period of 8 years. The number and nature of centres involved would require between 1-2 patients recruited per-centre per-month. At a conservative rate, we expect to recruit 60 patients in the Pilot Stage in 6 centres over 12-months.
- CHRONOS-B: A three-arm* MAMS RCT 1260 patients to be recruited over five years at a rate of 20 patients per month. The number and nature of centres involved would require between 1-2 patients recruited per-centre per-month. Conservatively, we expect to recruit 60 patients in the Pilot Stage in 6 centres over 12-months.

Short Title: IP4 - CHRONOS	Protocol No: 19CX5006	Sponsor: Imperial College London	Version: 5.0 Date: 13 th July 2022
			10 Gary 2022

^{*}Further arms may be added via substantial amendments

N.B. Patients observed in the Pilot Stage will be included in the Main Stage. In the event that the study does not proceed from Pilot to Main, patients recruited into the Pilot will be followed up for 6 months for safety monitoring.

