	Main study		
	CHRONOS-A 1190 patients		
	CHRONOS-B A three-arm MAMS RCT would require 1260 patients		
FEASIBILITY AND PILOT STUDY OBJECTIVES	To assess the feasibility of a trials framework that fits with existing patient and physician equipoise so that we can successfully and efficiently answer the next generation of research questions to evaluate medium-term outcomes following minimally invasive focal therapy in the treatment of clinically significant, non-metastatic prostate cancer.		
	 The embedded internal pilot objectives are: To determine patient acceptance to randomisation. To conduct an embedded qualitative study of patient and clinician acceptance and experience of the linked RCT CHRONOS design. To establish the feasibility of an economic evaluation alongside the main trial. To determine acceptability and completeness of resource use and utility measures (EQ-5D-5L). To identify the relevant NHS and non-NHS resource use to be collected alongside the main trial. To identify the relevant items to populate the Cost and Consequences framework. To perform preliminary analysis of pattern of missing data. 		
MAIN STUDY PRIMARY OBJECTIVES	CHRONOS-A To evaluate PFS rates of focal therapy alone compared to radical therapy (radiotherapy or surgery) in the treatment of non-metastatic clinically significant prostate cancer.		
	CHRONOS-B To evaluate FFS rates of focal therapy alone compared to focal therapy combined with other therapies as a neoadjuvant and/or adjuvant strategy.		
MAIN STUDY SECONDARY OBJECTIVES	Disease control Determine the histological, biochemical and oncological disease control for men undergoing radical therapy, focal therapy or focal therapy with neo/adjuvant treatments.		
	Adverse events and Functional Outcomes Determine the adverse events and functional outcomes after radical therapy, focal therapy or focal therapy with neo/adjuvant treatments		
	Health economics		

Short Title: IP4 - CHRONOS	Protocol No: 19CX5006	Sponsor: Imperial College London	Version: 5.0 Date: 13 th July 2022
-------------------------------	--------------------------	-------------------------------------	---

- To establish the NHS costs of the different interventions.
- To determine the Cost per QALYs (CUA), cost per PFS/FFS (CEA) and cost and consequences (CCA).
- To determine acceptability and completeness of resource use and utility measures (EQ-5D-5L).

Qualitative

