Based on an allocation ratio of 1:1 and a non-inferiority margin of 0.05 with a 0.85 PFS rate in the standard care arm (at median 5-years), power 0.80 and alpha 0.05, drop-out after randomisation of 5%, the overall required sample size is 1190 with 136 expected total number of events. Total recruitment and follow-up period will be 8 years. If recruitment rates were deemed to be high then the power could be adjusted to 0.90 and the total sample size will be 1660 with 189 expected total number of events. This will be on the advisement of the TSC. PFS for the main Stage will be defined as transition to salvage therapies or metastases or mortality related to prostate cancer.

CHRONOS-B main stages II and III: Using the latest update of –nstage-, with an allocation ratio of 1:1:1, we anticipate approximately 1200 patients are required over 5 years to observe 120 control arm failure-free survival (FFS) events within 7.6 years. This time will be dependent on observed FFS event rates and is based on an assumption of 20 patients recruited per month. This calculation gives 85% power at the efficacy stage analysis, to detect a hazard ratio (HR) of 0.67 and is based on 20% of patients having a FFS event by 3 years (30% by 5-years).

Table 1. Sample size calculations

	Short Title: IP4 - CHRONOS	Protocol No: 19CX5006	Sponsor: Imperial College London	Version: 5.0 Date: 13 th July 2022
١				10 Gary Lore

	Stage 1	Stage 2	Overall
Alpha	0.45	0.025	0.044
Power	95%	85%	83%
Critical HR (guidance for stopping early)	0.974		-
Control Arm Events	47	120	-
Accrual	20pts/m	20pts/m	20pts/m
Cumulative Patients	1003	1200	-
Time to analysis (years)	3.4	4.2	7.6

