6.6.2. CHRONOS-B

A three-arm* MAMS RCT 1260 patients to be recruited over five years at a rate of 20 patients per month. The number and nature of centres involved would require between 1-2 patients recruited per-centre per-month. Conservatively, we expect to recruit 60 patients in the Pilot Stage in 6 centres over 12-months.

[figure not shown]
*Further arms may be added, to the main trial, via substantial amendments

N.B. Patients observed in the Pilot Stage will be included in the Main Stage. In the event that the study does not proceed to the Main Stage following the analysis of the Pilot, patients will be followed up for a minimum of 3 months and will then revert to standard of care in which the clinical care provided to patients will not differ from the clinical follow-up stipulated in the study protocol.

We will consider adjusting the sample size for the main stage to incorporate the compliance and feasibility results from the analysis described in Section 9.

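### CHRONOS-B has two main-stage totals, 1260 and 1200; the calculation supports 1200, and 1260 does not fit its own accrual rate and duration

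*Protocol*

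**What the plan says.** Three places give 1260:

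- Protocol, Trial Summary, sample size: "A three-arm MAMS RCT would require 1260 patients".
- Protocol 8.1.1: "1260 patients to be recruited over five years at a rate of 20 patients per month".
- SAP 6.6.2, in the same terms: "MAMS RCT 1260 patients to be recruited over five years at a rate of 20 patients per month".

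Three places give 1200:

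- Protocol 8.1.2: "we anticipate approximately 1200 patients are required over 5 years to observe 120 control arm failure-free survival (FFS) events within 7.6 years". The timing "is based on an assumption of 20 patients recruited per month".
- Protocol 8.1.2, Table 1, last cumulative figure: "Cumulative Patients 1003 1200".
- Protocol 3.2, arm table: 400 in each of three arms, total 1200.

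Both totals go with five years of recruitment at 20 per month, and Protocol 8.2 repeats the five years. A 5% drop-out is stated in the CHRONOS-A calculation only. Protocol 8.1.1 and SAP 6.6.2 both say that pilot patients count towards the main stage.

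**The concern.** The headline summary and the SAP carry a target that is not the output of the power calculation, and the sentence giving 1260 contradicts itself on rate and duration. A funder costing the main stage, or a steering committee judging when accrual is complete, has two closing numbers that differ by 60 men, or three months of accrual at the planned rate. SAP 6.6.2 also says that the main-stage sample size may be adjusted in the light of the pilot, and an adjustment needs one agreed starting figure. The conflict leaves unclear whether CHRONOS-B allows for any loss to follow-up.

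**Working it through.** **Inputs.** From Protocol 8.1.2: 20 patients per month, 5 years, allocation 1:1:1, control-arm failure 20% by 3 years and 30% by 5 years, target hazard ratio (HR) 0.67. From Tables 1 and 2: 47 and 120 control-arm events, final one-sided alpha 0.025, stated power 85%.

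**1. Accrual.** N = rate × duration.

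- 20 × 60 = 1200 = 3 × 400, which agrees with 8.1.2, Table 1 and 3.2.
- 1260 / 20 = 63 months (5.25 years).
- 1260 / 60 = 21 per month.
- The difference is 60 men, and 60 / 1200 = 5%.

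**2. Does the design belong to 1200?** Assume uniform accrual of 80 men per arm per year for 5 years (20 × 12 / 3). Expected control events at calendar time t are 80 × ∫ F(t − u) du over entry times u from 0 to min(t, 5), where F is the cumulative failure probability. Two shapes for F are used:

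- piecewise exponential: hazard −ln(0.80)/3 = 0.0744 per year to year 3, then −ln(0.70/0.80)/2 = 0.0668;
- constant hazard of 0.0744 throughout.

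| Design | 120th control event, piecewise | 120th control event, constant |
|---|---|---|
| 1200, 60 months at 20 per month | 7.57 y | 7.37 y |
| 1260, 63 months at 20 per month | 7.41 y | 7.23 y |
| 1260, 60 months at 21 per month | 7.27 y | 7.10 y |

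The plan states 7.6 years. Of these, 1200 with the piecewise rates reproduces it. With the constant hazard, the 47th control event falls at 4.18 years, and 4.18 × 240 ≈ 1003 men accrued, which is Table 1's first cumulative figure. Table 1 prints 3.4 years for stage 1 and 4.2 for stage 2, which sum to 7.6; those entries look interchanged, but this does not affect the total.

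**3. Power at 120 control events.** With e₁ the expected research-arm events under HR 0.67 at the same date,

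power = Φ[(−ln 0.67 − 1.96 × √(2/120)) / √(1/120 + 1/e₁)].

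For 1200 with piecewise rates, e₁ = 85.3. The numerator is 0.4005 − 0.2530 = 0.1475, the denominator is √(0.00833 + 0.01172) = 0.1416, and the power is Φ(1.04) = 85.1%. The plan states 85%. For 1260, e₁ is 85.1 to 85.2 and the power is again 85.1%. Once 120 control events are in hand, the choice of total hardly matters to power.

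**4. Candidate origins of 1260.**

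- 1200 × 1.05 = 1260. This would be a 5% uplift by multiplication. Allowing for 5% loss by division gives 1200 / 0.95 = 1263.2.
- 1200 + 60 pilot patients = 1260. This counts the pilot patients twice, because they are already in the main stage.

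Neither route is documented for CHRONOS-B.

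**5. Effect of loss on 1200.** Assume that 5% of men contribute no follow-up, so 380 controls rather than 400 (76 per year). The 120th control event moves from 7.57 to 7.91 years (piecewise) or from 7.37 to 7.68 years (constant hazard). The delay is 0.31 to 0.34 year, about four months.

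**The case against.** The main stage is conditional on feasibility and funding, 8.1.2 calls its figure approximate, recruitment rates are to be reset from the pilot, and the SAP covers feasibility only. No SAP analysis or progression rule uses 1260. On this view a 5% difference in a provisional number is editorial. Much of that stands: nothing in the pilot turns on it, and the size is modest. It does not remove the contradiction. Table 1 and 3.2 give 1200 without qualification, and 1260 fails within its own sentence.

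It can also be said that 1260 is the same design with the pilot added, since 8.1.2 heads its calculation as main stages II and III. That reading is undocumented and conflicts with counting pilot patients in the main stage.

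A reader might go further and infer that, if some men are lost, recruiting 1200 forfeits the stated power. The documents do not support this. Protocol 8.3 triggers the final analysis by the number of control-arm events, and 8.1.2 says that the 7.6 years depends on observed event rates. Expected control events at 7.6 years would fall to 114.5–118.5 with 5% loss, against 120.5–124.7 without, but 7.6 years is a projection and not a cut-off.

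One limit applies to either total. The Trial Summary plans 12 months of pilot recruitment (60 men in CHRONOS-B) and a further 48 months. At 20 per month that gives 60 + 48 × 20 = 1020. Reaching 1200 after such a pilot takes 12 + 1140/20 = 69 months. Settling on 1200 therefore does not by itself reconcile the full recruitment timeline.

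**Conclusion.** The point holds as an inconsistency in a key planning figure. The CHRONOS-B total appears as 1260 in three places and 1200 in three others, nothing links them, and 1260 is incompatible with five years at 20 per month. The design outputs belong to 1200. The difference is 60 men (5%), or three months of accrual at the planned rate; it affects target, cost and timing and leaves power at about 85%. The origin of the extra 60 cannot be settled from the documents.

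The timing figures assume uniform accrual and the two hazard shapes above. The delay of about 0.3 year also assumes a 5% early loss, which the plan does not state for CHRONOS-B. The correction should be made before a main stage is funded.

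**What to change.** State one total everywhere. The figure that the calculation supports is 1200: replace 1260 with 1200 in the Trial Summary, Protocol 8.1.1 and SAP 6.6.2, and add to 8.1.2 that no drop-out is allowed for. Sections 3.2 and Table 1 then stand as they are.

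If an allowance is intended, state it and use a total divisible by three. For 5%, 400 / 0.95 = 421.1, rounded up to 422 per arm, or 1266. Change the accrual to match (1266 / 20 = 63.3, about 63 months at 20 per month, or a higher rate), and update 3.2, 8.1.2 and Table 1 as well as the three places that now say 1260.

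The first option costs wording in two documents and changes nothing in conduct. The second adds 66 men to the calculated total and about three months of accrual.
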